Electronic Alerts for Acute Kidney Injury Amelioration (ELAIA-1)
NCT Title and ID: Optimizing Electronic Alerts for Acute Kidney Injury
NCT02753751
April 24, 2020

SECTION V: RESEARCH PLAN

1. **Statement of Purpose:** State the scientific aim(s) of the study, or the hypotheses to be tested.

This study is designed to determine whether automated, electronic alerts for Acute Kidney Injury (AKI) will be effective at reducing progression of AKI, inpatient dialysis, and inpatient mortality rates in a hospitalized population.

2. **Background:** Describe the background information that led to the plan for this project. Provide references to support the expectation of obtaining useful scientific data.

Acute kidney injury (AKI) carries a significant, independent risk of mortality among hospitalized patients^{1,2}. Recent studies have demonstrated increased mortality among patients with even small increases in serum creatinine concentration^{3,4}. International guidelines for the treatment of AKI focus on appropriate management of drug dosing, avoiding nephrotoxic exposures, and careful attention to fluid and electrolyte balance⁵. Early nephrologist involvement may also improve outcomes in AKI⁶. Without appropriate provider recognition of AKI, however, none of these measures can be taken, and patient outcomes may suffer. AKI is frequently overlooked by clinicians⁷, but carries a substantial cost, morbidity and mortality burden.

Our research group conducted a pilot, randomized trial of electronic alerts for acute kidney injury in 2014.⁸ The trial, which randomized 2400 patients with AKI as defined by an increase in creatinine of 0.3mg/dl over 48 hours or 50% over 7 days, found that alerting physicians to the presence of AKI did not improve the course of acute kidney injury, reduce dialysis or death rates. Our pilot study demonstrates that there is clinical equipoise regarding the effectiveness of alerting, and that alerting to the presence of this condition (which does not have a treatment) is not standard of care.

Our pilot study was conducted in a single hospital, and the alert itself did not describe specific actions that a provider could take. In the present proposal, we seek to expand upon our prior study to determine if the use of an electronic alert will improve best practices for the care of hospitalized patients with AKI and/or improve rates of progression of AKI, dialysis or mortality in hospitalized patients across multiple hospital centers.

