Identification of subjects will be performed within the EPIC system, using a best-practice alert build developed by the Joint Data Analytics Team (JDAT) at Yale. The build will examine the most recent creatinine value, and compare it to the minimum value in the past 48 hours and 7 days. If the current value is 0.3mg/dl above the 48-hour minimum, or 50% higher than the 7-day minimum, the patient is defined as having AKI and he or she will be randomized as part of this trial. We have secured enthusiastic agreements from both JDAT and the Best Practice Alerts committee to engage in this line of research.

As this is an intervention assessing the influence of an alert system on provider behaviors surrounding AKI, we cannot inform patients of their participation in the study at the time of enrollment, as this would contaminate the randomized exposure.

While the unit of randomization is the patient, clinicians may also be considered subjects of this research. We will engage in pre-trial and periodic outreach to all clinicians who may be exposed to this study, informing them of the nature of the study, the fact that it is a randomized trial, and that alerts do not fire for all patients with AKI. We will additionally inform them that limited data is being collected regarding provider behavior. However, we will also make it clear that data subject to clinician behavior (such as AKI documentation) will NOT be linked to individual clinicians. All such data will only be analyzed in aggregate.

Intervention

Description

Patients randomized to the intervention will have an alert generated within the electronic health record, which will consist of a “pop-up” within the EMR when the provider assesses a patient record after the AKI-defining creatinine value has been registered. Providers who receive an alert include physicians, physician assistants, nurse practitioners, advanced practice registered nurses, fellows, physician/anesthesiologists, physician/sedation specialists, and residents. These alerts will be built by JDAT, who, as mentioned, have agreed to aid in the development of this study. The alert text will be displayed as follows:

BestPractice Advisory - Zzzcreatinineone, Ericastestpatient

Patient Safety (1)

AKI Alert:

Your patient has been identified as having ACUTE KIDNEY INJURY. Relevant creatinine values over the last seven days are listed below:

Most recent: **4 mg/dl**

Lowest in past 7 days: **2 mg/dl**

Highest in past 7 days: **4 mg/dl**

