Subjects will not be informed of their randomization status or participation in this trial as the trial could not be feasibly performed if subjects were told they were enrolled. We do not feel that post-facto informing of patients randomized in this trial is appropriate for several reasons. First, there is no guideline-based specific follow-up or intervention for acute kidney injury. Second, many patients may incorrectly assume that acute kidney injury is an iatrogenic condition, caused by poor medical care, when in fact it is indicative of the severity of the underlying medical condition. Finally, most patients will not be familiar with "acute kidney injury" and informing them of the presence of the condition may engender significant stress or anxiety without offering a tangible benefit.

All investigators will be blinded to treatment assignment until the end of the trial period. Care providers will, obviously, not be blinded to the intervention as they are receiving the alert. We will engage in both pre-trial and periodic teaching and discussion with all care providers (administered through short presentations at divisional conferences) to inform clinicians about the nature of the study, the fact that alerts do not fire for all patients with AKI, and to discuss specific factors that are being measured.

Primary Study Endpoints

Primary Outcome: The primary outcome will be a composite of progression to a higher stage of acute kidney injury (a doubling or tripling of creatinine from the pre-alert baseline), inpatient dialysis, or inpatient death at within 14 days of randomization.

-For patients who are discharged, we will impute 14-day creatinine using the last observation carried forward method.

Secondary Study Endpoints

1) Mortality Outcomes

- 14-day mortality
- Inpatient mortality

2) Dialysis outcomes

- 14-day dialysis
- Inpatient dialysis
- Discharge on dialysis

3) Renal Failure Outcomes

- Percent who progress to stage 2 AKI
- Percent who progress to stage 3 AKI
- Duration of AKI

4) Readmission Rate and Costs

- 30-day readmission rate
- Cost of index hospitalization

5) Individual “Best Practice” Outcomes, proportion achieved per patient in study arm during index hospitalization

- Contrast administration
- Fluid administration
- Aminoglycoside administration
- NSAID administration / cessation
- ACE inhibitor administration / cessation
- Urinalysis order
- Documentation of AKI
- Monitoring of creatinine
- Monitoring of urine output

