- Renal consult

6) Provider awareness outcomes

- Chart documentation of AKI (by post-discharge ICD-10 codes)
- Chart documentation of AKI (adjudicated)

Study Procedures

Randomization

Randomization will occur the moment AKI is detected by the electronic monitoring system within the EPIC best practice alert framework, as developed by JDAT. Beyond the primary intervention, no further tests or procedures will be performed on subjects in this trial. Randomization will be performed within the Epic system using a random number rule that is incorporated in the alert. This ensures that, upon meeting criteria, each patient is immediately and randomly assigned to an arm. Logic checks within the alerts ensure that once a patient is assigned to an arm, they remain on that arm for the remainder of their hospital stay.

Fourteen days post-randomization

Primary endpoint ascertainment

Thirty days post-randomization

Secondary endpoint ascertainment

Statistical Plan

Sample Size Determination

:

In our retrospective analysis of patients with AKI at 3 potential study hospitals, the composite outcome of death, dialysis, and progression of AKI was 24.5% (of 29,027 individuals with AKI). We believe a clinically meaningful relative reduction in this risk would be 20%, leading to an absolute rate of 19.6% in the intervention group. By enrolling 5,024 patients (2,512 in each group), we would have 90% power to detect a difference in outcome at least this extreme at a two-sided alpha of 0.05 as calculated using the Cochran-Mantel-Haenszel test (accounting for 6 hospital strata). We have elected to increase this number by 20% to account for potential contamination of the effect across

study arms, leading to a final sample size of 6,030 individuals. This sample size will also allow us to detect at least a 16% increase in best practices measures in the intervention group.

We must also consider that patients enrolled once in the trial will be excluded from enrolling again (on another admission, for example). While we don't have data on the rates of recurrent AKI we estimate that up to 20% of eligible patients may be excluded on this basis, which may slow recruitment somewhat.

In addition, pauses in trial enrollment may occur due to protocol changes / amendments based on feedback from providers and for quality improvement activities.

As such, we expect active enrollment, data acquisition, and outcome assessment to be completed over a three-year period.

Statistical Methods

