alert except “dismiss”, the alert would be suppressed for 48 hours for that particular provider. If multiple providers used the EHR to care for the same patient, each of them separately received the AKI alert when they opened the patient chart. Patients randomized to the usual care group generated “silent” alerts which did not display to providers but were tracked, allowing the study team to observe which types of providers opened the chart and how often.

The alert contained an option to add AKI to the patient’s problem list, as well as a link to an AKI order set (Supplemental Figure S2); the set included options for blood and urine testing and renal imaging, but were limited to tests and procedures considered minimal risk (ie IV fluid administration was not included). Providers at each of the study hospitals received education regarding AKI and the AKI alert system prior to study rollout during departmental conferences. Educational content was standardized and included the following elements: the definition and clinical relevance of AKI, the rates of best practice completion after AKI has developed, the study design, and how to interact with the alert (specifically focusing on the consequences of “accepting” or “disagreeing” with the alert. There was no formal curriculum on how to treat AKI in various situations, but providers were reminded of best practices such as urinalysis, urine output monitoring, AKI documentation, and subsequent creatinine measurement.

The development of the alert was an iterative process which used focus groups of providers to give feedback on design elements and wording as well as incorporating suggestions from the IRB. Providers were asked what relevant information should be shown in the alert, what responses could be given, and what elements should appear in the AKI order set (although, due to IRB restrictions, no drug or fluid interventions could be included). They were also asked about alert behavior such as the appropriate “lockout” – how long the alert should be repressed after a provider interacts with it. The final alert was presented to our local Best Practice Alert committee who provided formal approval. The alert was then piloted in “silent mode” for several months for quality assurance. During this time, no

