alerts were displayed, but patient data was captured to ensure they met the inclusion / exclusion criteria and to gather data around alert frequency. Once the system was demonstrated to be working correctly, with approval from the BPA committee, the trial was started.

Outcome Measures

The primary outcome was a composite of inpatient AKI progression, receipt of dialysis, or death within 14 days of randomization. AKI progression was defined as reaching a KDIGO creatinine stage higher than the stage present at randomization. Stages 2 and 3 AKI are defined as an increase in creatinine level by 2–2.9 times and an increase ≥ 3 times baseline, respectively. Receipt of dialysis was also considered to be AKI progression. Patients discharged in the 14-day outcome period were assumed to not meet any of these outcomes had they not met them at the time of discharge. Pre-specified secondary outcomes included the components of the primary outcomes and rates of various AKI care practices. These practices included administration of contrast, fluids, or a nephrotoxic agent (an NSAID, ACE inhibitor / angiotensin receptor blocker or aminoglycoside), ordering of a urinalysis, documentation of AKI, monitoring of creatinine and urine output, and ordering for a kidney consult. An assessment of per-hospital alert effects was also pre-specified.

Data Collection

Data were collected electronically from the electronic health record using a centralized data warehouse (Joint Data Analytics Team, Yale New Haven Health System). Data collected included admission characteristics, time-updated hospital location, laboratory data, medication exposures, vital signs, comorbidities (based on ICD-10 administrative coding) and hospital disposition. Cost information was obtained from a separate database. Direct costs reflect those associated with direct patient contact involving billable services (for example lab, nursing costs, and supplies). Total costs also include non-

billable support services such as medical records, human resources, accounting, support staff, utilities and dietary costs.

Statistical Analysis

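### Could more creatinine testing in the alert arm distort counted AKI progression enough to need a further analysis?

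*SAP*

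**What the plan says.** The primary outcome is AKI progression, dialysis or death within 14 days of randomization. In the SAP's Outcome Measures, "AKI progression was defined as reaching a KDIGO creatinine stage higher than the stage present at randomization", and "Receipt of dialysis was also considered to be AKI progression". The SAP's Patients section rules out urine output for classifying AKI. The protocol's Study Procedures (Randomization) states: "Beyond the primary intervention, no further tests or procedures will be performed on subjects in this trial". Apart from dialysis, then, progression rests on creatinines ordered in routine care.

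The Background asks "if the use of an electronic alert will improve best practices for the care of hospitalized patients with AKI", and the protocol's Secondary Study Endpoints list "Monitoring of creatinine" among those practices. Usual-care patients generated silent "alerts which did not display to providers but were tracked" (SAP, Intervention).

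Three further statements bear on the size of any effect:

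- Education before rollout covered all study hospitals, and in it "providers were reminded of best practices such as urinalysis, urine output monitoring, AKI documentation, and subsequent creatinine measurement" (SAP, Intervention).
- The protocol's Subject Recruitment and Screening section says: "While the unit of randomization is the patient, clinicians may also be considered subjects of this research". The same clinician can therefore treat patients in both arms.
- The SAP makes the components of the composite and the AKI care practices, creatinine monitoring included, pre-specified secondary outcomes. The protocol also lists 14-day mortality, 14-day dialysis and progression to stage 2 and to stage 3 separately.

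**The concern.** An outcome that exists only if someone measures it is open to detection bias when the intervention may change how often it is measured. If alerted clinicians repeat creatinine more often, brief crossings into stage 2 or 3 are caught in the alert arm and missed under usual care. Counted progression then rises with no change in the patients, which shifts the composite toward apparent harm or diluted benefit.

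This matters more because the SAP's Statistical Analysis section reports unexpected harm at non-teaching hospitals and looks for downstream explanations. Its list covers fluid overload markers, medications, renal consult, attending involvement and the burden of other alerts. Creatinine testing is absent. The primary test stratifies by hospital only, and the adjusted model uses characteristics at randomization. In these two documents, no analysis relates testing intensity to the primary result.

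**Working it through.** **Inputs.** The plan gives no figure for detection, so there is none to reproduce.

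- From the documents: control rate p = 24.5% (protocol, Sample Size Determination); 6,030 / 2 = 3,015 per arm; two-sided 0.04 for the primary outcome (SAP, Statistical Analysis); non-teaching hospitals 684 + 146 = 830 (SAP, Box 1), about 415 per arm.
- Assumed: RRp, the relative risk of counted progression due to testing alone, 1.012 to 1.048; f, the share of composite events known only through creatinine, 0.5 to 0.9; the same 24.5% in non-teaching hospitals, tested at two-sided 0.05.

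**Formulas.** Composite RR = 1 + f × (RRp − 1). With p2 = p × RR and m = (p + p2)/2:

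s0 = √[2m(1 − m)/n], s1 = √{[p(1 − p) + p2(1 − p2)]/n}

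P(significant harm) = Φ[(p2 − p − z × s0)/s1]. Hospital strata are ignored.

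**Composite shift.** Lowest: 1 + 0.5 × 0.012 = 1.006. Highest: 1 + 0.9 × 0.048 = 1.043.

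**False harm, whole trial (nominal 2%).**

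| RRp | f = 0.5 | f = 0.7 | f = 0.9 |
|---|---|---|---|
| 1.012 | 2.7% | 3.1% | 3.5% |
| 1.030 | 4.3% | 5.6% | 7.2% |
| 1.035 | 4.8% | 6.5% | 8.7% |
| 1.048 | 6.4% | 9.4% | 13.5% |

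Worst cell: p2 = 0.245 × 1.0432 = 0.2556 and s0 ≈ s1 ≈ 0.0112, so Φ[(0.0106 − 2.054 × 0.0112)/0.0112] ≈ 13.5%.

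**True benefit.** A true RR of 0.80 appears as 0.80 × 1.006 = 0.805 up to 0.80 × 1.0432 = 0.835. Power is 99.2% down to 95.7%, against 99.4% with no bias. (That exceeds the stated 90% because the plain two-proportion formula needs 1,503 per arm, not 2,512, a separate matter that does not affect this point.)

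**Non-teaching hospitals.** With n = 415 and z = 1.96, false harm is 2.8% at RR 1.006 and 5.4% at 1.043, against 2.5%. A 50% chance of significant harm needs a composite RR of about 1.25. Detection alone would then have to give RRp = 1 + 0.25/f, which is 1.28 at f = 0.9 and 1.50 at f = 0.5.

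**What a death-or-dialysis composite would add.** Control rate = 24.5% × (1 − f); power is for RR 1.20 at 0.05.

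| f | Control rate | Events per arm, whole trial | 95% CI at RR 1 | Power, whole trial | Power, non-teaching |
|---|---|---|---|---|---|
| 0.5 | 12.25% | 369 | 0.87-1.14 | 80% | 18% |
| 0.9 | 2.45% | 74 | 0.73-1.38 | 22% | 6% |

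In non-teaching hospitals the interval at RR 1 is 0.69-1.44 at f = 0.5 and 0.42-2.36 at f = 0.9, on about 51 and 10 events per arm.

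**The case for a change.** The case for a change is a fair one. The mechanism has some support: the alert links to a best-practices page, the order set offers blood tests, and the protocol's Risks section concedes that alerted providers may over-investigate or prolong the stay (it adds that the pilot did not show this). Creatinine monitoring is listed as a proportion achieved per patient. Such a measure could look equal in the two arms while draw frequency differs.

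The assumed inflation could also be too mild. Suppose usual care catches 90% of creatinine-only events, the alert arm catches all of them, and f = 0.9. Then p2 = 0.0245 + 0.2205/0.9 = 0.2695, the composite RR is 1.10, and false harm in the whole trial is 55%. Even then, RR 1.10 with 415 per arm gives about 12% in non-teaching hospitals.

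What stands is that these documents define no draw rate and do not relate testing to the primary result. What does not stand is the step from there to a needed amendment:

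- Neither the alert text nor the order-set description names repeat creatinine, and the reminder to repeat it was not confined to one arm. Nothing in the documents supports a capture gap as large as ten percentage points.
- Adding testing intensity to the mediation list would be hard to interpret. Draws rise because creatinine rises, and a Baron and Kenny analysis cannot separate a measurement artefact from a causal pathway.
- Death and dialysis, which need no creatinine threshold to be recorded, are already reported separately. Merging them adds little, and in non-teaching hospitals the result could only be descriptive.
- The SAP cites a published design description and says that its post hoc analyses are identified in the results. Neither can be seen here, so absence is established only for these two documents.

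**Conclusion.** Differential detection is possible but not shown. Under the assumed progression inflation of 1.2% to 4.8%, it moves the composite RR by 0.6% to 4.3%, leaves power for the planned effect at 95.7% or more, and would rarely create the non-teaching harm signal. A much larger capture gap would matter for the primary test, but only by assumption.

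The existing outputs would show the pattern to look for: a difference in creatinine monitoring with progression moving and death and dialysis not. Such a pattern would suggest detection without proving it, and its absence would not rule it out. The SAP already assigns the Mantel-Haenszel test to categorical variables and the Van Elteren test to continuous ones, and reports 95% confidence intervals throughout. An analyst can therefore express monitoring as draws per patient-day or time to next draw within the existing secondary outcome. A limitation sentence would change no result. The plan can stand as written on this point.

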We present descriptive statistics as median (interquartile range) for continuous variables and proportions for categorical variables. For the primary analysis, and all comparisons of categorical variables between the intervention and control group, we used the Mantel-Haenszel test, accounting for each hospital site as an individual stratum. The Mantel-Haenszel approach was used to obtain the pooled relative risks across hospital strata without adjusting for other baseline factors. As a sensitivity analysis, we used modified Poisson generalized estimating equations with a robust variance estimator to present the relative risk estimates adjusting for the following characteristics assessed at the time of randomization: age, sex, race, creatinine, blood urea nitrogen, white blood cell count, heart rate, respiratory rate, systolic and diastolic blood pressure, CHF, hypertension, diabetes, modified SOFA score, Elixhauser comorbidity score, and hospital.²⁻⁴ We used the Van Elteren test to compare continuous variables across the intervention groups, again accounting for hospital strata. To compare time-to-event between study groups, we used Cox proportional hazard regression with intervention as the independent variable, stratified by hospital, with censoring at 14-days after randomization. For individual hospital analyses, Kaplan-Meier curves were generated and log-rank tests were used. Patients discharged prior to 14 days without an outcome of interest were assumed to be free of that outcome at 14 days. Death was treated as a censoring event in analyses where death was not the outcome. We used Schoenfeld residuals to examine the proportional hazards assumption in Cox models; there were no violations.

We prespecified several secondary outcomes and subgroup analyses which we present without adjustment for multiple comparisons. We also pre-specified that each hospital would be analyzed

independently for evidence of heterogeneity of alert effects. Given the observed heterogeneity of effects, we explored mediators of that heterogeneity through the use of a generalized linear model in which the independent variables included an alert-by-hospital-type interaction term. Patient-level covariates were then added to this base model to determine if the significance of the interaction would be ablated by including these factors. Although patient characteristics did not account for the heterogeneous results, grouping hospitals into “teaching” vs. “non-teaching” did.

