Due to the unexpected finding of increased harm from the alert at non-teaching hospitals, we conducted several *post hoc* analyses, which are specifically identified in the results. To determine if the effect was mediated by actions downstream of the alert, we performed a formal mediation analysis using the method of Baron and Kenny (adjusted for age, sex, race, creatinine, blood urea nitrogen, white blood cell count, heart rate, respiratory rate, systolic and diastolic blood pressure, CHF, hypertension, diabetes, malignancy, modified SOFA score and Elixhauser comorbidity score at the time of randomization) of the following hypothesized mediators: markers of fluid overload, certain medications, the presence of renal consult, attending involvement in the care of the patient (as measured by the percent of alerts that went to attendings versus other providers), and the burden of other interruptive alerts (such as those for sepsis or medication interactions).^{5,6} The burden of other interruptive alerts was quantified as the number of other alerts received while the patient was eligible to be receiving AKI or Control alerts, divided by the amount of time they were eligible, leading to an average “non-aki alert per day” metric. Finally, we examined the rates of death and AKI progression in the time period 2 years prior to the start of the trial in each hospital to assess the degree of contamination across the study arms.

We assessed whether alert effectiveness changed over time by including an interaction term representing “time from first enrollment at this hospital” with the randomization status in a logistic regression equation. A significant p-value for this interaction term would suggest that the effect of the alert waxed or waned over time once it was “live” at a given hospital.

Our preliminary data suggested that 24.5% of patients would experience the composite outcome. We determined that a relative 20% reduction in this outcome (to 19.6) would be clinically significant. A sample size of 2,512 in each arm of the study achieves 90% power to detect this degree of change, but given the potential for contamination across study arms (whereby clinicians “learn” to identify and care for AKI over the course of the trial), which would tend to bias the results towards the null, we inflated the sample size by 20% to a total of 6,030.

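### A Kaplan-Meier curve of AKI progression or dialysis that censors deaths would overstate the 14-day inpatient risk and disagree with the SAP's own proportions

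*SAP*

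**What the plan says.** The SAP's Statistical Analysis section sets out the time-to-event methods. For the pooled comparison, "we used Cox proportional hazard regression with intervention as the independent variable, stratified by hospital, with censoring at 14-days after randomization". By site, "For individual hospital analyses, Kaplan-Meier curves were generated and log-rank tests were used". Two rules then cover patients who leave follow-up early:

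- Discharge: "Patients discharged prior to 14 days without an outcome of interest were assumed to be free of that outcome at 14 days".
- Death: "Death was treated as a censoring event in analyses where death was not the outcome".

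Under Outcome Measures, "The primary outcome was a composite of inpatient AKI progression, receipt of dialysis, or death within 14 days of randomization", and "Pre-specified secondary outcomes included the components of the primary outcomes and rates of various AKI care practices". Categorical outcomes are compared separately, by the Mantel-Haenszel test with hospital as stratum.

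Neither document mentions a cumulative incidence function, Gray's test or a subdistribution model. The SAP does not say which endpoints the Cox models and the by-hospital curves use. The protocol's Statistical Methods mention neither Cox nor Kaplan-Meier. For discharged patients, the protocol (Primary Study Endpoints) carries the last creatinine forward to day 14.

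**The concern.** The composite contains death, so the death-censoring rule cannot apply to it. The rule must be meant for outcomes without death, and the pre-specified components AKI progression and dialysis are the natural candidates.

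For those outcomes, death and discharge both end the chance of a recorded inpatient event, yet they are handled in opposite ways. A discharged patient stays in the denominator to day 14. A patient who dies is removed, as if progression or dialysis could still have followed. A Kaplan-Meier curve built this way does not estimate the share of patients who had the event by day 14. The same report could then carry two different 14-day figures for one component: the curve and the Mantel-Haenszel proportion.

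The Cox model raises a different issue. It gives a hazard ratio, not a risk, and censoring deaths is legitimate for a cause-specific hazard. Here, however, discharged patients remain in the risk set, so the estimate is not a pure in-hospital cause-specific hazard ratio. Deaths leave the risk set, so it is not a subdistribution hazard ratio either. A reader cannot tell what it estimates.

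**Working it through.** The documents give no figure for these analyses to reproduce, and no death, discharge or component rates by arm. All rates below are assumptions.

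**Formula.** Let E be the observed proportion with the event by day 14 and D the proportion who die without it. Read literally, the SAP's rules leave 1 − E(t) − D(t) at risk at time t, because discharged patients stay in. If event and death hazards keep a constant ratio over the 14 days, the cumulative hazard is −[E/(E+D)]·ln(1 − E − D), so

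1 − KM = 1 − (1 − E − D)^(E/(E+D)).

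The Mantel-Haenszel proportion and the Aalen-Johansen estimate at day 14 both equal E. For E = 15% and D = 5%: 0.80^0.75 = 0.846, so 1 − KM = 15.4%.

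| True E | D = 5% | D = 10% | D = 15% |
|---|---|---|---|
| 2% (dialysis) | 2.05% (+2.6% relative) | 2.11% (+5.4%) | 2.17% (+8.4%) |
| 4% (dialysis) | 4.10% (+2.6%) | 4.22% (+5.4%) | 4.34% (+8.5%) |
| 15% (progression) | 15.41% (+2.7%) | 15.85% (+5.7%) | 16.33% (+8.9%) |
| 20% (progression) | 20.56% (+2.8%) | 21.16% (+5.8%) | 21.82% (+9.1%) |

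**Timing of deaths.** If every death came at time zero, 1 − KM would be E/(1 − D), a relative excess of D/(1 − D): 5.3% at D = 5% and 17.6% at D = 15%. Late deaths shrink the excess towards zero.

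**Role of the discharge rule.** Suppose 65% are discharged (X = 0.65), with E = 15% and D = 5%. If discharge were censored as well, 1 − KM would be 1 − (1 − E − D − X)^(E/(E+D+X)) = 1 − 0.15^(0.15/0.85) = 28.5%, against 15.4% under the SAP's rule. Keeping discharged patients limits the excess; it does not cause it.

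**Between arms, equal true incidence.** With E = 15% in both arms and deaths of 5% and 10%, the ratio of the curves is 15.85/15.41 = 1.03 where the true ratio is 1.00.

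**Between arms, equal event hazard.** Take an event hazard of 0.006 per day in both arms, death hazards of 0.020 and 0.032, and a discharge hazard of 1/6. Let Λ be the sum of the three. Then E = (event hazard/Λ)(1 − e^(−14Λ)), and D likewise.

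- First arm: Λ = 0.1927, E = 2.90%, D = 9.7%, 1 − KM = 3.06% (+5.2%).
- Second arm: Λ = 0.2047, E = 2.76%, D = 14.7%, 1 − KM = 2.99% (+8.3%).

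The ratio of true incidences is 0.95 and the ratio of the curves is 0.98. The arm with more deaths has the larger overstatement, but the curves lie closer together than the incidences do.

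**Cox model.** A simulation of 2,000,000 patients per arm used an event hazard of 0.035 per day in both arms, death hazards of 0.012 and 0.024 (deaths 6% and 11%) and a discharge hazard of 0.14. Under the SAP's rules the hazard ratio was 0.98. The in-hospital cause-specific ratio is 1.00 by construction, and the ratio of incidences was 0.95. With a shared frailty for event and death, the hazard ratio was 0.96 and the incidence ratio 0.94.

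**The case against.** Much of the case for leaving the plan alone stands.

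- **The affected curves may not exist.** The SAP names no endpoint for the by-hospital curves. If they show the composite or death, nothing is wrong with them.
- **The 14-day component risks are available elsewhere.** The Mantel-Haenszel comparison already counts a death without dialysis as no dialysis, which is the right inpatient proportion.
- **Censoring deaths is a standard choice for a hazard question.** Log-rank and Cox ask whether the alert changes the event rate among those still alive. Gray's test and Fine-Gray answer another question and have their own trap: an arm with more deaths can look better because more of its patients die first. This argues against replacing the log-rank test.
- **The size is small.** In the equal-hazard example the overstatement is 0.15 points in one arm and 0.23 in the other, a difference of 0.08. Hospitals 5 and 6 enrolled 684 + 146 = 830 patients (SAP, Box 1). With an assumed 415 per arm and 3% risk, the standard error of a difference is √(2 × 0.03 × 0.97/415) = 1.2 points, about 15 times larger.

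Two stronger readings are tempting. A reader might infer that the method creates a 2 to 3% difference between arms. It does not follow: that figure is a difference in overstatement (5.2% against 8.3%), and with equal event hazards the curves differ less than the true incidences.

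A reader might also link the distortion to the SAP's remark "Due to the unexpected finding of increased harm from the alert at non-teaching hospitals". The documents give no deaths by arm, so they do not show where the distortion would be larger. The mediators examined are fluid overload, medications, renal consult, attending involvement and other alerts; progression and dialysis curves are not among them.

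What the objection does not answer is that the stated rule, applied to a non-fatal component, yields a curve that contradicts the SAP's own proportion, and that neither the endpoints nor the meaning of the hazard ratio is stated.

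**Conclusion.** The point holds for any Kaplan-Meier curve of AKI progression or dialysis drawn under the stated rules. Such a curve overstates the observed 14-day inpatient risk by about 3% relative at 5% deaths, rising to 8 to 9% at 15%. In absolute terms that is 0.05 to 1.8 points over the table above. These figures rest on assumed rates, a constant ratio of event to death hazards, and a literal reading of the discharge rule.

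At similar event rates the excess is larger where deaths are more frequent. It need not be larger in points if event rates differ: E = 20% with D = 5% gives 0.56 points, E = 10% with D = 6% gives 0.32. The target here is inpatient risk; against a target that included events after discharge, the net direction is unknown.

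The Cox hazard ratio is not shown to be materially biased; its fault is an unlabelled estimand. A reader might take the point as a challenge to the main result, but the composite counts death as an event and is tested by Mantel-Haenszel, so the primary analysis is untouched. Importance is minor to moderate, for secondary results only.

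**What to change.** In the SAP's Statistical Analysis section, and in the report:

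1. Name the endpoint of every Cox model and every by-hospital curve.
2. For AKI progression and dialysis, replace Kaplan-Meier curves by Aalen-Johansen cumulative incidence with death as a competing event and discharged patients event-free to day 14. The day-14 value then agrees with the Mantel-Haenszel proportion.
3. Keep the log-rank and Cox results for these components, labelled as death-censored hazard comparisons with discharged patients kept in the risk set.
4. Optionally add Gray's test or a Fine-Gray estimate beside them, with the caution that more deaths in an arm can make it look better on those measures. The SAP withholds P-values for secondary analyses other than safety outcomes, so the curves with confidence intervals matter more than the extra test.
5. Leave the composite and death analyses as they are.

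The cost is a few sentences, standard code in the software the SAP already names, and a little more reporting. No new data are needed.
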